Calistar A vs. Calistar S - Comparative Cohort Retrospective Analysis of Single Incision POP Systems

ID: CaSCaA Version number: Ver_03 Date: 28/05/2018

NCT03715803

Study Protocol

CALISTAR A VS CALISTAR S – COHORT RETROSPECTIVE ANALYSIS

(Ver_03 - 28/05/2018)

PROTOCOL APPROVAL

Responsible/Protocol Author/PI

(dd/mm/yyyy)

This protocol has been designed in accordance with the principles of Good Clinical Practices, EN-ISO 14155, Declaration of Helsinki and other applicable regulatory requirements.

SIGNATURE PAGE

CALISTAR A VS CALISTAR S – COHORT RETROSPECTIVE ANALYSIS

(Ver_03 - 28/05/2018)

I have read this protocol and agree to adhere to the requirements. I will provide copies of this protocol and all pertinent information to the study personnel under my supervision and my hospital ethics committee / institutional review board (EC/ORB). I will discuss this material with them and ensure they are fully informed regarding the device and the conduct of the study according to this protocol, applicable laws, and applicable regulatory requirements including Good Clinical Practices.

Clinical Site Name

Site Principal Investigator Signature

Date

Site Principal Investigator Printed Name

TABLE OF CONTENTS

SIGNATURE PAGE	3
Table of contents	4
GENERAL INFORMATION	5
BIBLIOGRAPHY	7

GENERAL INFORMATION

Protocol ID	
Short title	CALISTAR A VS CALISTAR S – Cohort retrospective analysis
EudraCT number	N/a
Version	3.0
Date	28/05/2018
Coordinating investigator/project leader	Dr. [name], Gynecologist
	Hospital Universitario Austral, Department of gynaecology
	[name],
	Argentina
	[name]
	[contact]
Principal investigators	See Annex 1
Sponsor	N/a
Product	Calistar A and Calistar S Single Incision POP System from
	Promedon. The products which are the object of this study have
	the approval according the CE-Guideline 93/42/EWG.
Objective	To compare the initial outcomes and complication of a high
	weight and a low weight meshes, Calistar A and Calistar S,
	respectively, implanted through a single incision to treat anterior
	and apical prolapses.
Study design	Multicentre, post-market, retrospective, two arms, non-
	randomized comparative study.
Study population	Adult female
Main study parameters/ primary	Effectiveness of Calistar S and Calistar A will be assessed by cure
endpoints	criteria of Barber, that is:
	- Lowest point of POP-Q < 0 (no points beyond the hymen)
	- No subjective bothersome symptoms (absence of vaginal bulge
	symptoms)
	- No re-treatment/interventions on year post procedure.

Secondary endpoints	The secondary endpoint is defined as the objective assessment of
	POP by POP-Q. POP-Q staging will be compared pre- and post-
	operative.
	The subjective outcome is defined as the assessment of
	subjective symptoms resulting from POP by validated quality of
	life (QoL) questionnaires (improvement of the QoL of the subjects
	compared to the baseline values):
	- Pelvic Floor Distress Inventory (PFDI 20) to assess the impact of
	urinary, prolapse and colorectal distress post-operative.
	- Pelvic Organ Prolapse/ Urinary Incontinence Sexual
	Questionnaire (PISQ-12) to evaluate sexual function in women
	with pelvic organ prolapse and/or urinary incontinence post-
	operative.
	- Patient Global Impression to evaluate patient satisfaction with
	the experience and the result of procedure.
	Type of surgery and operative time will be compared for both
	pelvic floor systems repair.
Safety endpoints	Operative complications such as bladder injury and blood loss will
	be evaluated. Complications related to the use of meshes such as
	vaginal pain, infection and mesh erosion will be assessed.
Inclusion criteria	Female;
	Anterior and apical prolapse Stage 3 (according to POP-Q) or
	more with or without SUI;
	Primary or recurrent treatment with Calistar S or Calistar A;
	At least 6 months follow-up
Exclusion criteria	Recurrent vaginal infections;
	Chronic colorectal diseases (chronic nonspecific ulcerative colitis,
	diverticulitis, diverticulosis, Chron's disease, irritable bowel
	syndrome, familial polyposis);
	Presence of any coagulopathies;
	Impairment of the immune system or any condition that
	compromises recovery;
	Prior irradiation;
	Chronic pelvic pain

BIBLIOGRAPHY

- 1. SCENIHR. Opinion on The safety of surgical meshes used in urogynecological surgery. 2015. 105 p.
- Amid PK. Classification of biomaterials and their related complications in abdominal wall hernia surgery. Hernia [Internet]. 1997;1(1):15–21. Available from: http://link.springer.com/10.1007/BF02426382

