#### STUDY ENDPOINTS

The primary outcome of this retrospective study is to evaluate the effectiveness of Calistar A or Calistar S pelvic floor repair systems. Cure is defined according to Barber criteria (1):

- Lowest point of POP-Q < 0 (no points beyond the hymen)
- No subjective bothersome symptoms (absence of vaginal bulge symptoms)
- No re-treatment/interventions on year post procedure.

The secondary outcomes of this retrospective study are the objective (anatomical) and subjective ([disease specific] quality of life) outcome of anterior and apical prolapses treated with Calistar A or Calistar S.

Other outcomes are follow-up time, blood loss during surgery, operating time, operative and postoperative complications, any recurrent prolapse according to the POP-Q classification, repeat surgery for prolapse, mesh erosion, mesh shrinkage, vaginal pain.

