#### STATISTICAL ANALYSIS

Demographic and baseline characteristics will be summarized using standard descriptive methods.

The primary outcome is a compound score and will be reported as the percentage of patients that meet all 3 criteria (with the confidence interval around that percentage). Paired t-test for continuous variables and non-parametric (Wilcoxon or Mann-Whitney U) test for percentages differences between pre- and post-operative will be calculated. Sensitivity analysis will be performed for the primary endpoint.

Secondary outcomes will be presented as percentages with 95% CI for dichotomous outcomes, means with 95% confidence intervals for continuous normally distributed variables and medians

with interquartile ranges for non-normally distributed variables. Differences between baseline and post-operative follow-up for the questionnaire scores will be calculated. Comparison between Calistar A and Calistar S pelvic floor repair systems will be performed.

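### Type of surgery is listed as an endpoint to compare between devices, and no adjustment for it is planned, so a difference in procedure mix can be read as a device effect on operating time, blood loss or complications

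*Protocol*

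**What the plan says.** The protocol's General Information table describes the design as "Multicentre, post-market, retrospective, two arms, non"-randomised. Its Secondary endpoints entry ends by saying that "Type of surgery and operative time will be compared for both" systems. Neither document defines type of surgery. The Inclusion criteria entry admits women with prolapse of stage 3 or "more with or without SUI", and both primary and recurrent cases.

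The SAP does not carry type of surgery forward. Under Study Endpoints it states: "Other outcomes are follow-up time, blood loss during surgery, operating time, operative and postoperative complications", and it continues with items that include mesh erosion and vaginal pain.

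The SAP's Statistical Analysis section covers the device contrast in one sentence: "Comparison between Calistar A and Calistar S pelvic floor repair systems will be performed". Two further sentences are relevant. The first is "Demographic and baseline characteristics will be summarized using standard descriptive methods", which is descriptive only. The second is "Sensitivity analysis will be performed for the primary endpoint", which gives no content and does not reach operating time, blood loss or complications.

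The SAP's Hypothesis section says that the low-weight mesh reduces complications while effectiveness is maintained.

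**The concern.** The surgeon and the woman's condition settle the type of surgery at or before the operation. It can differ between the two cohorts, but mesh weight does not cause that difference. Listing it beside operating time treats it as a result. Its natural use here is as a covariate, because a longer or more complex operation can take more time, lose more blood and carry more complications whichever mesh is used.

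Nothing in the design balances procedure mix between devices. Women are not randomised. They come from several centres, and implants span January 2011 to April 2017. Women with and without SUI, and primary and recurrent cases, are all eligible. The protocol evidently expects type of surgery to vary, since it plans to compare it.

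What is at stake is how the safety and operative results are interpreted. Complications are half of the stated hypothesis, and a crude comparison could credit or charge either mesh with a difference that belongs to the operations performed.

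**Working it through.** **The plan's own figure.** The only number nearby is the total of 200 subjects at significance level 0.05 and at least 80% power (SAP, Sample Size). It cannot be reproduced, because no effect size, event rate, SD, margin or split by device is given. For orientation, 100 per arm at two-sided 0.05 gives 80% power for a standardised mean difference of about 0.40. The plan states no figure on procedure mix.

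**Assumed inputs (none is in the documents).**
- 100 women per arm, two-sided 0.05, no true device effect
- SD of operating time within a type of surgery: 20 minutes
- added time d for an operation that includes a further procedure: 10 to 40 minutes
- share of such operations in the two cohorts, q1 and q2: 30% vs 50%, or 40% vs 50%

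**Formulas.**
- Spurious difference = d × (q2 − q1)
- Crude SE = √{[20² + d²·q1(1 − q1)]/100 + [20² + d²·q2(1 − q2)]/100}
- With z = difference/SE, the probability of a falsely significant result = 1 − Φ(1.96 − z) + Φ(−1.96 − z)

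Worked case, 30% vs 50% and d = 30: the difference is 30 × 0.20 = 6 minutes. The SE is √[(400 + 900 × 0.21)/100 + (400 + 900 × 0.25)/100] = √(5.89 + 6.25) = 3.48, so z = 1.72 and the probability is 0.41.

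| Shares | d (min) | Spurious difference (min) | Crude SE | z | Falsely significant |
|---|---|---|---|---|---|
| 30% vs 50% | 10 | 2 | 2.91 | 0.69 | 11% |
| 30% vs 50% | 20 | 4 | 3.14 | 1.28 | 25% |
| 30% vs 50% | 30 | 6 | 3.48 | 1.72 | 41% |
| 30% vs 50% | 40 | 8 | 3.92 | 2.04 | 53% |
| 40% vs 50% | 10 | 1 | 2.91 | 0.34 | 6% |
| 40% vs 50% | 20 | 2 | 3.16 | 0.63 | 10% |
| 40% vs 50% | 30 | 3 | 3.52 | 0.85 | 14% |

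Equal shares give q2 − q1 = 0, hence no bias and the nominal 5%.

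**After adjustment (30% vs 50%).** The correlation between device and type of surgery is 0.5 × 0.20/√(0.4 × 0.6) = 0.204. The adjusted SE is 20 × √(2/100)/√(1 − 0.204²) = 2.83/0.979 = 2.89 minutes, whatever the value of d. Adjustment removes this bias and does not widen the interval. The gain in precision is negligible at d = 10 (2.91 to 2.89) and clear at d = 40 (3.92 to 2.89).

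**Complications.** Assume mesh erosion of 5% without a further procedure and 10% to 20% with one. At 30% vs 50%, the lower end gives 5 + 5 × 0.30 = 6.5% vs 5 + 5 × 0.50 = 7.5%, a spurious 1 point. The upper end gives 5 + 15 × 0.30 = 9.5% vs 5 + 15 × 0.50 = 12.5%, a spurious 3 points. Blood loss is not quantified, because neither a scale nor an SD is available.

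**The case against.** The strongest reply is that comparing type of surgery between devices is useful. In a non-randomised study it is a balance check, it would expose the imbalance in question, and it does not prevent adjustment. That stands: the tabulation should stay. What remains at fault is its standing as an endpoint and its absence from the outcome comparisons.

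Second, type of surgery is undefined, and neither document mentions concomitant procedures or a second mesh. A reader might infer that some operations certainly included a sling or another implant, and that its erosion or pain will be charged to Calistar. The documents do not support this. SUI at entry does not show that it was treated at the same operation, and primary or recurrent describes treatment history. Eligibility makes a varied procedure mix plausible and no more.

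Third, type of surgery is not the only candidate. SUI, primary or recurrent status, POP-Q stage and centre may also predict these outcomes, and no adjustment is specified for any outcome, including the primary. This is one instance of a wider gap. It is still worth making separately, because the protocol already names this variable and gives it the wrong role.

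Fourth, the SAP refers to sections 6.2.1 and 6.2.2, which are not in the available protocol text, and part of the SAP was unavailable. A definition could lie there. The Statistical Analysis section, however, appears complete and contains no adjustment.

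**Conclusion.** The point holds in conditional form. The protocol treats type of surgery as an endpoint, and the available SAP plans no adjustment for it, so operating time, blood loss and complications compared as written can carry differences in procedure mix.

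It would go too far to say that such differences are, or will be, read as device effects. That requires an imbalance which the documents neither state nor quantify. The size depends wholly on assumptions: for operating time, from nothing under balance, through 1 to 3 minutes and 6% to 14% false significance at 40% vs 50%, to 2 to 8 minutes and 11% to 53% at 30% vs 50%. For erosion, the assumed example gives 1 to 3 points. The bias can favour either device.

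The outcomes concerned are secondary, safety and other outcomes; this point does not concern the primary cure endpoint. Because complications belong to the hypothesis and the remedy is cheap, the change should be made.

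**What to change.** - Define type of surgery: Calistar alone, or Calistar with each other procedure done at the same operation.
- Take it out of the Secondary endpoints and report it by device as a baseline or operative characteristic.
- In the SAP, estimate the device differences in operating time and blood loss with type of surgery as a covariate or stratum.
- Count all mesh complications for each device. Also report them stratified by type of surgery, including whether another mesh was implanted at the same operation if that is recorded.
- Do not exclude complications on the basis of where the chart places them. Retrospective attribution, with no blinding to device described, could under-count harm, and poorly localised events such as vaginal pain would be the first to drop out.

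The cost is wording in both documents and one model term or stratum. Strata for rare complications will be sparse, so those results should be descriptive. The protocol already plans to compare the variable, so some form of it must be abstracted. No list of data items is available to show that each further procedure is recorded, and if it is not, chart abstraction would need an extra field. Adjustment removes only the bias that comes from type of surgery; other differences between the cohorts need their own treatment.

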#### SAMPLE SIZE

For this retrospective study all patients who received a Calistar A or Calistar S implant between January 1st 2011 and April 30th 2017 and who meet all the inclusion criteria describe in *6.2.1 Inclusion criteria* will be eligible for enrolment. Patients who meet at least one of the exclusion criteria listed in *6.2.2 Exclusion criteria* will be excluded. A total of 200 subjects are planned to be included in this clinical study, distributed among research centres, gives the possibility of having results with a significance level of 0.05 (95%) with a minimum discriminant power of 80%. The multicenter aspect will guarantee a sufficient number of patients to be included in the study.

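### Entry at 6 months does not fit a cure criterion that reads as one year, and no method for unequal follow-up is stated for complications that build up over time

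*Protocol*

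**What the plan says.** The protocol's inclusion criteria require "At least 6 months follow-up". Cure, worded identically in the protocol and in the SAP (Study Endpoints), has three parts:

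- no POP-Q point beyond the hymen, with no time point;
- no bulge symptoms, with no time point;
- "No re-treatment/interventions on year post procedure", most naturally read as one year.

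The SAP (Statistical Analysis) reports the percentage of women meeting all three. It adds: "Sensitivity analysis will be performed for the primary endpoint". It does not say what that analysis contains.

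Eligible women received a "Calistar A or Calistar S implant between January 1st 2011 and April 30th 2017" (SAP, Sample Size). Follow-up time appears only in a list: "Other outcomes are follow-up time, blood loss during surgery". The same list includes recurrence, repeat surgery, mesh erosion, mesh shrinkage and vaginal pain. For such outcomes the SAP says "Secondary outcomes will be presented as percentages with 95% CI for dichotomous outcomes". For the devices it says only "Comparison between Calistar A and Calistar S pelvic floor repair systems will be performed".

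**The concern.** There are three linked gaps.

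1. **Scoring.** A woman last seen between 6 and 12 months without failure meets the entry rule, but her re-treatment status at one year is unknown. Nothing says whether she counts as cured, failed or missing. In a retrospective study that choice could be made after the results are known.
2. **Timing.** Two criteria may be read at any visit. If the latest examination is used, a woman re-treated after year 1 and examined afterwards can count as cured. The protocol's objective calls the outcomes initial, so an early examination is also a possible reading, and under it this case does not arise. The plan does not choose.
3. **Time at risk.** The SAP's hypothesis is fewer complications with Calistar S at maintained effectiveness, in a non-randomised comparison. Crude percentages of events that accumulate favour whichever device was followed for less time. Intra-operative outcomes such as blood loss are unaffected.

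**Working it through.** **The plan's own figure.** The SAP states: "A total of 200 subjects are planned to be included in this clinical study", with 80% power at a 0.05 level. No effect size, event rate, margin or split between devices is given, so 200 cannot be reproduced. Nothing below depends on its being right. I assume 100 per device and also try a 60/140 split.

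**Possible follow-up (from the documents).** To the protocol date, 28 May 2018:
- first eligible implant, 1 January 2011: 7.40 years;
- last eligible implant, 30 April 2017: 393 days = 1.08 years = 12.9 months.

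One year is therefore possible by the calendar for every woman. The entry rule still accepts 6 months of actual follow-up.

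**Women last seen at 6-12 months (assumed share f = 10-30%).**
- Counting them as complete: if 2-6% of them have an unseen re-treatment, cure is overstated by 10% × 2% = 0.2 to 30% × 6% = 1.8 points.
- Leaving the rule open: with cure c in the rest, worst case is (1 − f)c and best case is (1 − f)c + f. For f = 0.20 and c = 0.85 these are 0.80 × 0.85 = 68% and 68% + 20% = 88%. The width equals f, so it is 10-30 points.

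**Re-treatment after year 1 (assumed hazard h = 2-3% per year, follow-up T = 2-5 years).** The share is exp(−h) − exp(−hT):
- h = 0.02, T = 2: 1.9%;
- h = 0.03, T = 5: 11.0%.

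This is the upper bound on misclassification by that route. If 25-75% of these women are later examined and meet the other two criteria, it is 0.5-8.2 points.

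**Complications, identical devices.** Under a constant hazard, risk = 1 − exp(−ht), with every woman on a device given the same t. The result is the chance that a two-sided 5% two-proportion test (pooled null standard error SE0, normal approximation) is significant in favour of the shorter-followed device: Φ[(p1 − p2 − 1.96·SE0)/SE1].

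Example, h = 3%, 5 versus 2 years, 100 each: p1 = 1 − exp(−0.15) = 13.9% and p2 = 1 − exp(−0.06) = 5.8%. The difference is 0.0811, SE0 = 0.0422 and SE1 = 0.0418, so Φ[(0.0811 − 0.0827)/0.0418] = 48%.

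| Follow-up | 1%/year | 3%/year | 5%/year |
|---|---|---|---|
| Equal | 2.5% | 2.5% | 2.5% |
| 3 v 2 years, 100/100 | 6.5% | 11.5% | 16% |
| 5 v 2 years, 100/100 | 20% | 48% | 69% |
| 5 v 2 years, 60/140 either way | 12-24% | 36-48% | 57-65% |

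**If events come early.** Take an eventual risk of 12% with 80% of it in year 1: risk = 0.12 × (1 − exp(−1.609t)).
- 5 versus 2 years: 12.0% versus 11.5%, chance 3.2%.
- Limit case, 5 years versus the 6-month minimum: 12.0% versus 6.6%, chance 26%.

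**Choice of test.** The SAP names none. Fisher's exact test lowers the 1% per year values to 9% (5 versus 2 years) and 1.3% (3 versus 2 years). At 3-5% per year and 5 versus 2 years it still gives 40-63%.

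**The case against.** The strongest reply is that the bias is conditional. Nothing shows that follow-up differs by device, the implant window is the same for both, and no text says crude percentages will be tested. Follow-up time is a listed outcome, so it may well be described by device. The large figures need a three-year gap and events that keep arriving. With early events the excess almost disappears, and with Fisher's test the low-hazard figures shrink. All of this stands: the numbers show what could happen and do not forecast it. Describing follow-up, however, does not account for it, and the only dichotomous summary named is a percentage.

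On the primary outcome, the 10-30 point width merely restates the assumed share, and simply counting these women as complete moves cure by at most 1.8 points. That is true. The problem is that the endpoint has no scoring rule, and the sensitivity analysis has no content to fill the gap. The route by which a re-treated woman counts as cured needs several assumptions and only one reading of the timing. That part is a request to state the timing.

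The SAP also refers to sections 6.2.1 and 6.2.2, which are not in the public text. They concern eligibility. The endpoint and analysis sections, where a scoring rule or comparison method would be expected, are available and give none. The conclusion is limited to that text.

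**Conclusion.** The concern holds and must be fixed before analysis. The textual mismatch is certain, subject to reading the third criterion as one year. If that reading is wrong, no horizon for re-treatment is stated at all, and the endpoint still needs correction. How many women it affects is unknown.

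The time-at-risk problem is a real gap of unknown direction and size. Under the assumed hazards it ranges from negligible (3.2% against 2.5%, early events, 5 versus 2 years) to large (48-69% at 3-5% per year for the same follow-up). Unequal follow-up alone could therefore create or hide the hypothesised reduction in complications.

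**What to change.** 1. **Reconcile entry and endpoint.** Score all three cure criteria at one common time, for example 12 months with a stated visit window. Treat women last seen earlier without failure as missing, and make best-case and worst-case analyses the content of the planned sensitivity analysis. Raising entry to 12 months would also remove the mismatch, but risks selecting women by their follow-up.
2. **Re-treatment.** Count any re-treatment before the scored examination as failure.
3. **Complications.** Compare outcomes that accumulate by a censoring-aware method from the implant date (for example Kaplan-Meier and Cox), or over the same fixed window for both devices. Report follow-up by device.

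The text change is short: endpoint timing in the protocol, and the scoring rule and comparison method in the SAP. The cost lies in the charts. A 12-month rule leaves a missing primary outcome for women last seen at 6-12 months, and a woman whose implant is 12.9 months old may still have no charted 12-month visit. Event dates must be abstracted and may be imprecise for erosion and shrinkage, which are dated when found. Where they are, the fixed window is the simpler choice.

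### The 6-month follow-up entry rule makes entry depend on what happens after surgery, and it is applied even to outcomes settled in the operating room

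*Protocol*

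**What the plan says.** - **Entry rule.** The Inclusion criteria row of the Protocol's General Information table ends with "At least 6 months follow-up". It does not say whether this means time under observation or time elapsed since the implant.
- **Where it applies.** The SAP, Sample size, starts from "all patients who received a Calistar A or Calistar S implant between January 1st 2011 and April 30th 2017" and limits eligibility to those "who meet all the inclusion criteria describe in" its section 6.2.1. That section is not in the public text, so any fuller wording cannot be checked. As published, one cohort serves every endpoint.
- **Outcomes fixed at surgery.** The Safety endpoints row of the Protocol says that "Operative complications such as bladder injury and blood loss will" be examined. The Secondary endpoints row adds type of surgery and operative time. The SAP, Study endpoints, has a matching list: "Other outcomes are follow-up time, blood loss during surgery, operating time, operative and postoperative complications".
- **Outcomes that can be settled early.** Cure includes the condition "No re-treatment/interventions on year post procedure". Mesh erosion and repeat prolapse surgery are listed among the other outcomes.
- **Design.** The Study design row reads "Multicentre, post-market, retrospective, two arms, non"-randomized. The SAP hypothesis is that the lighter mesh lowers complications without losing effectiveness.
- **What is absent.** No population of all implanted women is defined for operative safety. No rule covers an event recorded in a woman with short follow-up, and no count of such women by mesh is planned. The SAP names a sensitivity analysis for the primary endpoint only and does not describe it.

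**The concern.** Whether a woman has 6 months of follow-up is known only after treatment, and it may be related both to how she fared and to which mesh, centre and period she belongs to. Using it as an entry condition selects the cohort on a post-treatment event.

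For operative outcomes the condition gains nothing, because the result is complete on the day of surgery. For re-treatment or erosion, a woman with an event at month 2 who then moved to another hospital is a known event, and the rule discards it. Complications are half of the study's hypothesis and the arms are not randomized, so nothing in the design makes loss equal between meshes. Women whose charts are never abstracted cannot be recovered by later adjustment.

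**Working it through.** **1. Is the rule an administrative cut-off?** The implant window closes on 30 April 2017 (SAP, Sample size). The Protocol is marked "Ver_03 - 28/05/2018". From 30 April 2017 to 28 May 2018 is 393 days, and 393 / 30.4375 = 12.9 months. Every eligible woman had more than 12 months of elapsed time by then. If follow-up means elapsed time, the rule excludes nobody. If it means observed follow-up, which is the more natural reading, it acts only on women whose observation stopped early.

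**2. The plan's own figure.** The 200 subjects at 0.05 and 80% power cannot be reproduced, because no rates, effect size, margin, sidedness or allocation are given. Assuming 100 per arm and a two-sided test, 80% power is reached at differences such as 20% against 6.6%. This serves only as a scale for what follows.

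**3. Operative outcome (all inputs assumed).** Let p be the true bladder injury rate, L the loss before month 6 among uninjured women and Li the loss among injured women. The rate among women kept is

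p(1 − Li) / [p(1 − Li) + (1 − p)(1 − L)].

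With p = 4% and L = 15%:

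| Li | Calculation | Observed rate |
|---|---|---|
| 5% | 0.038 / (0.038 + 0.816) | 4.45% |
| 30% | 0.028 / (0.028 + 0.816) | 3.32% |
| 50% | 0.020 / (0.020 + 0.816) | 2.39% |

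**4. Any complication, and cure (assumed).** Let c be the true risk in all implanted women, f the share dropped, and r the risk in dropped women divided by the risk in kept women. The observed risk is c / [(1 − f) + f·r].

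- c = 20%, f = 10%: r = 2 gives 0.20/1.10 = 18.2%; r = 1 gives 20%; r = 0.5 gives 0.20/0.95 = 21.1%. The bias can go either way or vanish.
- True cure 80% (failure 20%): f = 10%, r = 2 gives 1 − 0.20/1.10 = 81.8%; f = 30%, r = 3 gives 1 − 0.20/1.60 = 87.5%.

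**5. Comparison of meshes, true risk 15% in both arms (assumed).**

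| f in A, S | r in A, S | Observed A | Observed S | S − A |
|---|---|---|---|---|
| 10%, 10% | 3, 3 | 0.15/1.2 = 12.5% | 12.5% | 0 |
| 10%, 30% | 2, 2 | 0.15/1.1 = 13.6% | 0.15/1.3 = 11.5% | −2.1 points |
| 10%, 30% | 3, 3 | 12.5% | 0.15/1.6 = 9.4% | −3.1 points |
| 30%, 10% | 3, 3 | 9.4% | 12.5% | +3.1 points |
| 20%, 20% | 3, 1 | 0.15/1.4 = 10.7% | 15.0% | +4.3 points |

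Equal loss with an equal link to outcome leaves equal risks equal. Otherwise a false difference appears, and its sign follows the pattern of loss.

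**6. Would counting every early event as a failure repair cure?** Not alone. Assume 235 women with a true failure rate of 20%. Of these, 35 are lost at random, and 10% of the 35 have a recorded early event. The 200 followed women contribute 40 failures. Adding the 3.5 early events while leaving out the event-free lost women gives (40 + 3.5) / (200 + 3.5) = 21.4%, a bias of 1.4 points where the existing rule has none. Keeping all 235 and bounding the 31.5 event-free lost women gives cure between 160/235 = 68.1% and (160 + 31.5)/235 = 81.5%, a range that contains the true 80%.

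**The case against.** The strongest reply has four parts.

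- **The wording may be harmless.** If the criterion means time since implant, nobody is excluded. This cannot be ruled out while section 6.2.1 is unavailable. It is a reason to clarify the text.
- **A minimum follow-up is legitimate for cure.** Cure needs a postoperative POP-Q and a symptom assessment. This stands, and the requirement can stay for the main cure analysis. It does not extend to outcomes complete at surgery.
- **The numbers are assumed and modest.** This also stands. Nothing in the documents supports any particular loss rate. With 100 per arm and a 4% rate, the standard error of a difference is √(2 × 0.04 × 0.96 / 100) = 2.8 points, larger than the spread of 4.45 − 2.39 = 2.1 points in step 3. Unlike sampling error, however, selection bias does not shrink as more women are enrolled, and a confidence interval does not show it.
- **The extra charts may not be few.** The documents give neither their number nor their availability.

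A reader might also infer that the rule removes all women with operative complications or early failures. It does not: a woman with a bladder injury or a re-treatment at month 2 who was followed to month 6 stays in.

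**Conclusion.** The point holds as a design weakness of unknown size. On the observed-follow-up reading, entry is conditioned on a post-surgery event for every endpoint, and no published passage recovers the excluded women. The defect is clearest for bladder injury, blood loss, operating time and type of surgery, where the condition serves no purpose.

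The documents do not support a claim that the comparison is biased, or biased in favour of either mesh. That would require loss, or its link to outcome, to differ by mesh, and no figure on this is given. The false differences of 2.1 to 4.3 points in step 5 show what unequal patterns could do under assumed inputs; they are not estimates for this study. The conclusion rests on reading follow-up as observed follow-up and on the published text being complete on this point. It merits a cheap improvement and does not invalidate the study.

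**What to change.** 1. State whether the 6 months refers to observed follow-up or to time since implant.
2. Enter every woman implanted in the window who meets the pre-operative criteria, and analyse operative outcomes in all of them.
3. Report, by mesh, the number with under 6 months of follow-up and any events recorded among them.
4. Keep the follow-up requirement for the main cure analysis. Give the sensitivity analysis already named in the SAP a content: include all women with short follow-up, count known early failures as not cured, and bound event-free women both ways (all cured, then all not cured).
5. Analyse erosion and re-treatment by time-to-event methods with censoring at last contact, so that early events and event-free time both count. This still assumes that loss of contact is unrelated to the later risk of an event, so the counts in item 3 should be read beside it.

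The cost is a few lines in the Protocol and SAP and the abstraction of some extra charts. The documents do not give their number. If 15% of women had short follow-up, 200 / 0.85 ≈ 235 implanted women would mean about 35 more. The cure bounds will be wide if many event-free women were lost, but that uncertainty already exists and the current plan does not show it.
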